5.2. Exclusion Criteria

1. Clinically significant (CS) abnormalities in medical history according to Investigator judgement (e.g., previous acute coronary syndrome within 6 months of Screening, major non-pituitary surgery within 2 months of Screening) or from Screening physical examination (PE)
2. Patients who received surgery for pituitary adenoma within the last 3 months before the trial, and/or planning to receive surgery during the trial
3. Patients who received radiotherapy for pituitary adenoma within the last 2 years before the trial, and/or planning to receive radiotherapy during the trial
4. Patients with a pituitary tumor that, per Investigator judgment, is worsening (e.g., either growing, or at risk of compressing or abutting the optic chiasm or other vital structures) as assessed by pituitary/sellar MRI protocol at Screening or within 3 months of Screening. CT scan is allowed if MRI is contraindicated

5. Evidence of decompensated cardiac function per medical judgement and/or New York Heart Association (NYHA) Class 3 or 4
6. Clinical evidence of symptomatic hyperprolactinemia that would necessitate treatment
7. Symptomatic cholelithiasis, and/or choledocholithiasis
8. Intentionally left blank
9. Patients with history of hypoglycemia unawareness (who have had > 3 severe episodes in the past 6 months) or documented reactive hypoglycemia
10. Screening laboratory results as follows, or any other CS abnormalities in Screening laboratory values that would render a patient unsuitable for inclusion (abnormalities may be retested for eligibility purposes)
 - a. UPCR ≥ 500 mg/g. In the event of urine protein/creatinine ratio (UPCR) above this threshold eligibility may be confirmed by a quantitative total urine protein measurement of < 1000 mg/24 hr
 - b. Positive test (including trace) for blood on urinalysis. In the event of a positive test eligibility may be confirmed with urine microscopy showing ≤ 5 red blood cells per high power field
 - c. alanine aminotransferase (ALT) or aspartate aminotransferase (AST) $> 1.5 \times$ ULN; alkaline phosphatase (ALP) $> 3 \times$ ULN; Total bilirubin $\geq 1.5 \times$ ULN. Patients with Gilbert's syndrome may have total bilirubin $\geq 1.5 \times$ ULN if only the indirect bilirubin is elevated $>$ ULN and the ALT/AST is not greater than the ULN.

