 - d. eGFR < 45 mL/min/1.73 m² as determined by the Chronic Kidney Disease-Epidemiological Collaboration (CKD-EPI) equation for creatinine clearance OR serum creatinine > 1.8 mg/dL in males and > 1.5 mg/dL in females
 - e. Platelet count $< 125,000$ mm³
 - f. Abnormal thyroid function tests must be discussed with the Sponsor Medical Monitor or Designee
 - g. HbA1c $> 10\%$
 - h. Abnormal morning cortisol test demonstrating symptomatic adrenal insufficiency based on Investigator judgement
11. Active infection requiring systemic antiviral or antimicrobial therapy that will not be completed prior to Study Day 1
12. Unwillingness to comply with study procedures, including follow-up, as specified by this protocol, or unwillingness to cooperate fully with the Investigator
13. Active infection with human immunodeficiency virus (HIV), hepatitis C (HCV) or hepatitis B (HBV) diagnosed by initial serology testing and confirmed with RNA testing, or prior treatment for HCV. Patients at Screening who test positive by serology, but negative by RNA may be allowed in consultation with the Sponsor Medical Monitor or Designee
14. Malignancy within 5 years, except for basal or squamous cell carcinoma of the skin, carcinoma *in situ* of the cervix, follicular Stage 1 or papillary thyroid cancer that has been successfully treated; patients that have been treated with curative intent and which have

no recurrence within 5 years may also be eligible if approved by the Sponsor Medical Monitor or Designee

15. Treatment with another investigational drug, biological agent, or device within 1 month of Screening, or 5 half-lives of investigational agent, whichever is longer
16. Treatment with any non-ION- or ISIS-oligonucleotide (including small interfering ribonucleic acid [siRNA]) at any time or prior treatment with an ION- or ISIS-oligonucleotide within 9 months of Screening. Patients that have previously received only a single-dose of an ION- or ISIS-oligonucleotide as part of a clinical study may be included as long as duration \geq 4 months has elapsed since dosing. This exclusion does not apply to vaccines (neither mRNA nor viral vector vaccines)
17. History of bleeding diathesis or coagulopathy
18. Recent history of, or current drug or alcohol abuse that could affect study compliance per Investigator judgment

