6.1.1. Screening

Written informed consent for the study will be obtained prior to the performance of any study-related procedures including screening procedures. Race and ethnicity data will be

collected as part of the demographic information for all screened patients during the Screening Period. Up to a 6-week Screening Period is provided for completing screening assessments and determining patient eligibility for the study.

During the 6 weeks, site will need to gather disease history relating to acromegaly and pituitary adenoma, and the results of the most recent MRI. MRI of the sellar will need to be performed before randomization if there is no prior MRI within the last 3 months prior to Screening. If the MRI is contraindicated, then a CT Scan may be performed. In addition, an echocardiogram will be conducted, if there is no prior echocardiogram within the last 3 months prior to Screening.

Individuals may be disqualified if the result of any laboratory test is outside the range specified in the eligibility criteria (Section 5.1 and 5.2) or, if no range is specified, is abnormal and CS as judged by the Investigator or the Sponsor Medical Monitor or Designee. During the Screening Period, screening results may be retested (Home Health Care Visit Option can be used) for assessment after discussion with the Sponsor Medical Monitor or Designee for eligibility purposes.

IGF-1 can be repeated once and averaged to determine eligibility if the initial result is between 1.1–1.3 × ULN, or between 5–5.3 × ULN.

Sponsor Medical Monitor or Designee review of eligibility is required for patients to enter the Treatment Period. Qualified patients will be randomized and proceed to the Treatment Period Week 1, Day 1 Assessments.

Screen failed patients may be re-screened 1 more time after the Investigator feels the reason for screen failure has resolved.

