8.5.1. Safety Monitoring Rules for Liver Chemistry Tests

The following rules are adapted from the draft guidance for industry, “Drug-Induced Liver Injury: Premarketing Clinical Evaluation,” issued by the U.S. Department of Health and Human Services, Food and Drug Administration, July 2009. For a definition of Baseline please refer to guidance in Section 8.5 above.

In the event of an ALT or AST measurement that is $> 3 \times \text{ULN}$ or the greater of $2 \times \text{baseline}$ value or $3 \times \text{ULN}$ if the baseline value was $> \text{ULN}$ at any time during the study (Treatment or Post-Treatment Period), the initial measurement(s) should be confirmed as described above. Additional, confirmatory measurements should also be performed if ALT or AST levels increase to $5 \times \text{ULN}$.

Frequency of Repeat Measurements: Patients with confirmed ALT or AST levels $> 3 \times \text{ULN}$ or the greater of $2 \times \text{baseline}$ value or $3 \times \text{ULN}$ if the baseline value was $> \text{ULN}$ should have their liver chemistry tests (ALT, AST, ALP, international normalized ratio [INR], and total bilirubin) retested at least once-weekly until ALT and AST levels become $\leq 1.5 \times \text{ULN}$ or $< 1.5 \times \text{baseline}$ value if the baseline value was $> \text{ULN}$.

Further Investigation into Liver Chemistry Elevations: For patients with confirmed ALT or AST levels $> 3 \times \text{ULN}$ or the greater of $2 \times \text{baseline}$ value or $3 \times \text{ULN}$ if the baseline value was $> \text{ULN}$, the following evaluations should be performed:

1. Obtain a more detailed history of symptoms and prior and concurrent diseases
2. Obtain further history for concomitant drug use (including nonprescription medications, herbal and dietary supplement preparations), alcohol use, recreational drug use, and special diets
3. Obtain a history for exposure to environmental chemical agents and travel
4. Serology for viral hepatitis (hepatitis A virus [HAV] immunoglobulin M [IgM], hepatitis B surface antigen [HBsAg], HCV antibody, cytomegalovirus [CMV] IgM, and Epstein-Barr Virus [EBV] antibody panel)
5. Serology for autoimmune hepatitis (e.g., antinuclear antibody)

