8.6.1. Stopping Rules for Liver Chemistry Elevations

In the event of laboratory results meeting the following criteria, **and the event is without an alternative explanation as discussed with the Sponsor Medical Monitor** (or appropriately qualified Designee), dosing of a patient with ISIS 766720 will be stopped permanently; values that are not confirmed due to failure to retest or missing lab values will be presumed confirmed:

1. ALT or AST $> 8 \times$ ULN, which is confirmed
2. ALT or AST $> 5 \times$ ULN, which is confirmed and persists for ≥ 2 weeks
3. ALT or AST $> 3 \times$ ULN or the greater of $2 \times$ baseline value or $3 \times$ ULN if the baseline value was $>$ ULN, which is confirmed **and** total bilirubin $> 2 \times$ ULN or INR > 1.5
4. ALT or AST $> 3 \times$ ULN or the greater of $2 \times$ baseline value or $3 \times$ ULN if the baseline value was $>$ ULN with the new appearance (i.e., onset coincides with the changes in hepatic enzymes) of fatigue, nausea, vomiting, right upper quadrant pain or tenderness, fever, rash, and/or concomitant eosinophilia ($>$ ULN)

8.6.2. Stopping Rules for Renal Function Test Results / Temporary Stopping Rules for Renal Function Test Results

In the event of a persistent elevation that is observed over 2 consecutive weeks, for either of the 2 criteria below, dosing of a patient with ISIS 766720 will be suspended temporarily:

1. Serum creatinine increase that fulfills all of the following: ≥ 0.3 mg/dL (26.5 μ mol/L) **and** $\geq 40\%$ above baseline creatinine values **and** $>$ ULN (refer to definition of baseline in Section 8.6)
2. Proteinuria, UPCR > 750 mg/g for baseline > 200 mg/g, or $4 \times$ baseline for baseline < 200 mg/g that is confirmed by repeated UPCR or by a quantitative total urine protein measurement of > 1.0 g/24 hour

The possible dosing re-initiation or follow-up schedule for any events meeting either of these criteria will be determined by the Investigator **in consultation with** the Sponsor Medical Monitor or Designee.

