Appendix A. Schedule of Procedures – Treatment Period

Study Period	Screen ¹	Treatment Period ²																				
Study Week	-6 to -1	1	3	5	7	9	11	13	15	17	21	25	27	29	33	37	41	45	49	53	57	
Study Day	-42 to -1	1	15	29	43	57	71	85	99	113	141	169	183	197	225	253	281	309	337	365	393	
Visit Window ± Day	0		3	5	7	7	7	7	7	7	7	7	7	7	7	7	7	7	7	7	7	
Home Health Care Visit Option ¹⁶				X		X		X		X	X			X	X	X		X	X	X		
Informed Consent	X																					
Inclusion/Exclusion	X																					
Medical History	X																					
Disease History	X																					
MRI/CT of sellar	X ³																	X ³			X ³	
Echocardiogram	X ³																					X ³
AcroQoL		X			X			X				X			X			X			X	
ASTS-M		X			X			X				X			X			X			X	
EQ-5D		X			X			X				X			X			X			X	
SF-36		X			X			X				X			X			X			X	
Ring Size Measurement	X	X			X			X				X			X			X			X	
Body Weight and Height ⁴	X	X		X	X	X	X	X	X	X			X			X			X			X
Vital Signs ⁵	X	X	X	X	X	X	X	X	X	X	X	X	X	X	X	X	X	X	X	X	X	
Physical Exam ⁶	X	X		X	X		X		X			X			X			X			X	
ECG (12-Lead)	X	X		X	X		X		X			X			X			X			X	
Adverse Events	X	X	X	X	X	X	X	X	X	X	X	X	X	X	X	X	X	X	X	X	X	
Concomitant Medications	X	X	X	X	X	X	X	X	X	X	X	X	X	X	X	X	X	X	X	X	X	
HIV, Hepatitis B & C	X																					

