APPENDIX B. LIST OF LABORATORY ANALYTES

Appendix B. List of Laboratory Analytes

Based on emerging data from this or future studies, additional tests not listed below may be performed on stored samples to better characterize the profile of ISIS 766720 or other similar oligonucleotides.

Clinical Chemistry Panel	Screening Tests	Hematology	Inflammatory
● Sodium	● HBsAg	● Red blood cells	● hs-CRP ⁴
● Potassium	● Hepatitis C antibody	● Hemoglobin	
● Chloride	● HIV antibody	● Hematocrit	Urinalysis
● Bicarbonate	● Serum βhCG	● MCV, MCH, MCHC	● Color
● Total protein	● FSH (females only) ¹	● Platelets	● Appearance
● Albumin		● White blood cells (WBC)	● Specific gravity
● Calcium	Coagulation	● WBC Differential (% and absolute)	● pH
● Magnesium	● aPTT (sec)	– Neutrophils	● UPCR
● Phosphorus	● PT (sec)	– Eosinophils	● UACR
● Glucose	● INR	– Basophils	● Protein
● BUN		– Lymphocytes	● Blood
● Creatinine	PD Panel (*Partial PD Panel)	– Monocytes	● Ketones
● Cholesterol	● IGF-1* ⁵		● Urobilinogen
● Uric Acid	● GH*	Thyroid Panel	● Glucose
● Total bilirubin	● GHBP*	● TSH	● Bilirubin
● Direct (conjugated) bilirubin	● ALS	● Free T4	● Leukocyte esterase
● Indirect (unconjugated) bilirubin	● IGFBP3	● Total T3	● Nitrate
● ALT			● Microscopic examination ³
● AST	Glycemic Panel	Bone Biomarkers ⁴	
● ALP	● HbA1c	● Urinary N-telopeptide crosslink (NTX)	Lipid Panel
● Creatine kinase	● Glucose	● Bone specific alk phos	● Total Cholesterol
● GGT	● Glycated albumin	● Amino terminal propeptide of Type 1 procollagen (PINP)	● LDL cholesterol
● Lipase			● HDL cholesterol
Pituitary Axis	OGTT Plasma Assessments	Pharmacokinetics ²	● Triglycerides
● Morning Cortisol (before 9:00 AM)	● Glucose	● ISIS 766720 levels in plasma	● VLDL
● ACTH	● Insulin		● Lp(a)
● Prolactin	● c-peptide	Immunogenicity ²	Cardiac Biomarkers ⁴
● SHBG	● GH	Anti-ISIS 766720 antibodies	● Cardiac troponin I
● Testosterone			● NT-proBNP
● FSH (females only)			
● LH			

¹ Only to confirm post-menopausal state at Screening, if required

² Plasma PK and immunogenicity samples may also be used for profiling of drug binding proteins, bioanalytical method validation purposes, stability assessments, metabolite assessments, or to assess other actions of ISIS 766720 with plasma constituents

³ Will be performed on abnormal findings unless otherwise specified

⁴ May be analyzed

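### Exclusion 13 names RNA testing as the confirmatory test for hepatitis B, a DNA virus, so for HBV the stated test neither confirms nor rules out active infection

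*Combined protocol and SAP*

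**What the plan says.** Criterion 13 has the same wording in the protocol synopsis and in Section 5.2. It excludes active infection with HIV, hepatitis C or "hepatitis B (HBV) diagnosed by initial serology testing and confirmed with RNA testing". The next sentence reads: "Patients at Screening who test positive by serology, but negative by RNA may be allowed in consultation with the Sponsor Medical Monitor or Designee". Neither sentence treats hepatitis B differently from the other two viruses.

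Appendix A schedules one virology line, "HIV, Hepatitis B & C", at Screening only. Appendix B lists three viral tests under Screening Tests: HBsAg, "Hepatitis C antibody" and HIV antibody. It lists no nucleic-acid test for any of them.

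Section 6.1.1 adds a general check: "Sponsor Medical Monitor or Designee review of eligibility is required for patients to enter the Treatment Period". Sections 3.4.1 and 4.2 also call for that review.

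**The concern.** The confirmatory step is meant to separate current infection from a serological trace of past infection. For HIV and hepatitis C, an RNA assay after a positive antibody does that. For hepatitis B it does not, because HBV viremia is measured as HBV DNA. HBsAg is also a viral antigen, not an antibody left by past exposure, so a positive HBsAg followed by a negative RNA result gives no reason to think the infection is inactive.

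Two things are at stake. One is the safety of a patient who might enter with unmeasured HBV viremia. The other is the reading of liver results. The protocol has detailed ALT/AST monitoring (8.5.1), dose-adjustment guidance (8.5.1.1) and permanent stopping rules (8.6.1), and the treatment groups described are all dose levels of the study drug. No untreated arm shows the background course of liver enzymes.

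**Working it through.** The plan states no figure to reproduce. The check sets the sections side by side.

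**1. Does the confirmatory test fit each virus?**

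| Virus | Genome | Screening test (Appendix B) | Confirmation (criterion 13) | Measures viremia? |
|---|---|---|---|---|
| HIV | RNA | HIV antibody | RNA | Yes |
| Hepatitis C | RNA | Hepatitis C antibody | RNA | Yes |
| Hepatitis B | DNA | HBsAg | RNA | No |

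The genome column is basic virology. The rest comes from the protocol.

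**2. What follows if the criterion is applied literally?** An HBsAg-positive patient counts as having active hepatitis B only if an RNA test is also positive. If it is negative, the patient falls under the exception and may be discussed with the medical monitor. No HBV DNA result is needed at either step.

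**3. Is an HBV DNA test required elsewhere?** Section 6.1 refers to Appendices A, B and C for the required procedures. None of them names one. The work-up for confirmed ALT/AST elevation in Section 8.5.1 asks for "hepatitis B surface antigen [HBsAg], HCV antibody" and other serology, again without HBV DNA.

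**4. What other safeguards apply at entry?**

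- Sponsor eligibility review (3.4.1, 4.2, 6.1.1): applies to every patient, but specifies no HBV test.
- Exclusion 10: any other clinically significant screening laboratory abnormality; a matter of judgement.
- Exclusion 10c: ALT or AST above 1.5 × ULN; does not test for HBV.
- Exclusion 11: an infection whose systemic antiviral treatment will not be finished before Day 1; depends on the patient needing treatment.
- Exclusion 25: any other unsuitable condition; discretionary.

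Each could keep such a patient out. None measures HBV viremia.

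**5. What happens to ALT/AST attribution if one such patient is treated?** Section 8.6.1 stops dosing permanently when the thresholds are met "and the event is without an alternative explanation as discussed with the Sponsor Medical Monitor". In a patient known to be HBsAg-positive, hepatitis B is always available as an explanation. The 8.5.1 work-up only repeats an HBsAg test already known to be positive, and there is no pre-dose HBV DNA value for comparison. A drug effect could be put down to HBV. In the other direction, SAP Section 3.7.4 counts confirmed ALT/AST above 3 and 5 × ULN without regard to cause, so an HBV-related rise would enter those tables.

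**6. How many patients?** The number admitted is

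screened × P(HBsAg-positive) × P(RNA-negative) × P(passes the other exclusions) × P(sponsor agrees).

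The documents give none of these terms. Purely as an illustration, assume 60 screened and 0.1% to 3% HBsAg-positive. The first two terms then give 60 × 0.001 = 0.06 to 60 × 0.03 = 1.8. That counts HBsAg-positive patients at Screening. It is an upper bound on admissions under those assumptions, because the remaining factors are each at most 1.

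**7. What weight would one admitted patient carry in the safety tables?** Safety uses the Safety Set, so the 12 evaluable patients per group (1/12 = 8.3%) is not the right denominator. Assuming equal groups and that all randomized patients are dosed:

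- about 40 in three groups: 40/3 = 13.3 per group, and 1/13.3 = 7.5%;
- about 30 in two groups (the Amendment 3 alternative): 30/2 = 15 per group, and 1/15 = 6.7%.

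These are indicative only. Amendment 3 says allocation need not be equal, and SAP Section 3.7 summarizes safety by maximum dose received.

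**The case against.** The strongest reply is that this is loose drafting. RNA may stand for nucleic-acid testing in general, and the laboratory may in practice run HBV DNA. The documents neither say so nor rule it out. Appendix B's silence does not settle the matter: it also omits the RNA tests that criterion 13 plainly requires for HIV and hepatitis C, and several serologies named in 8.5.1. It is not a complete list of conditional tests. This stands, and it means that the fault lies in the criterion's wording and that no actual laboratory failure has been shown.

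Three stronger readings are tempting and go beyond the documents.

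- **That a negative RNA result clears an HBsAg-positive patient.** It does not. The exception is permissive and requires consultation, every patient needs sponsor review, and exclusions 10, 10c, 11 and 25 still apply.
- **That the plan cannot detect hepatitis B.** HBsAg is scheduled for Screening, so the positive result is in front of the investigator and the sponsor. What fails is the confirmatory step.
- **That HBV-related enzyme rises would be taken for a drug signal.** Known HBsAg positivity supplies an alternative explanation under 8.6.1. The supportable claim is that the clause becomes hard to apply, with error possible in either direction.

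The safeguards limit the consequence. They do not repair the criterion, because the medical monitor is asked to decide on a result that does not bear on the question.

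**Conclusion.** Wrong as written; low severity. For hepatitis B, criterion 13 names a confirmatory test that is uninformative about active infection and makes the entry exception depend on it. This rests on the literal wording, on HBV being a DNA virus, and on no section naming an HBV DNA test.

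Few patients are likely to be affected, and the documents do not allow the number to be derived. One admitted patient would be roughly 7% of a dose group under equal allocation. The sample size, the primary endpoint and its analysis are unaffected. The issue is patient safety and the interpretation of ALT/AST rises.

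**What to change.** In criterion 13, in both the synopsis and Section 5.2, name the confirmatory nucleic-acid assay for each virus, so that the hepatitis B assay measures HBV DNA. Reword the exception so that it refers to the virus-specific result instead of to RNA for all three. Add the reflex tests to Appendix B, or state there that conditional tests are not listed. If the laboratory already runs HBV DNA, this only records existing practice.

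The sponsor should also check whether any HBsAg-positive patient entered under the exception and, if so, identify that patient alongside the ALT/AST results. This remains useful if enrollment has closed.

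The cost is a minor protocol amendment, which under Section 12.1 must be notified to the regulatory authority and IEC/IRB and approved by them if judged likely to affect patient safety or trial conduct, plus the correct reflex assay in the few serology-positive patients. No analysis changes.

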6. STUDY PROCEDURES

6.1. Study Schedule

All required study procedures are outlined in [Appendix A](#), [Appendix B](#), and [Appendix C](#).

6.1.1. Screening

Written informed consent for the study will be obtained prior to the performance of any study-related procedures including screening procedures. Race and ethnicity data will be

collected as part of the demographic information for all screened patients during the Screening Period. Up to a 6-week Screening Period is provided for completing screening assessments and determining patient eligibility for the study.

During the 6 weeks, site will need to gather disease history relating to acromegaly and pituitary adenoma, and the results of the most recent MRI. MRI of the sellar will need to be performed before randomization if there is no prior MRI within the last 3 months prior to Screening. If the MRI is contraindicated, then a CT Scan may be performed. In addition, an echocardiogram will be conducted, if there is no prior echocardiogram within the last 3 months prior to Screening.

Individuals may be disqualified if the result of any laboratory test is outside the range specified in the eligibility criteria (Section 5.1 and 5.2) or, if no range is specified, is abnormal and CS as judged by the Investigator or the Sponsor Medical Monitor or Designee. During the Screening Period, screening results may be retested (Home Health Care Visit Option can be used) for assessment after discussion with the Sponsor Medical Monitor or Designee for eligibility purposes.

IGF-1 can be repeated once and averaged to determine eligibility if the initial result is between 1.1–1.3 × ULN, or between 5–5.3 × ULN.

Sponsor Medical Monitor or Designee review of eligibility is required for patients to enter the Treatment Period. Qualified patients will be randomized and proceed to the Treatment Period Week 1, Day 1 Assessments.

Screen failed patients may be re-screened 1 more time after the Investigator feels the reason for screen failure has resolved.

